 Ribavirin: 200 mg tablet

Doses:	ABT-450/r/ABT-267: 150/100/25 mg QD ABT-333: 250 mg BID Ribavirin: weight-based dosing 1000 or 1200 mg divided twice daily or adjusted for renal impairment subjects
Mode of Administration:	Oral
Reference Therapy:	Not applicable
Dose:	Not applicable
Mode of Administration:	Not applicable
Duration of Treatment:	Subjects will receive ABT-450/r/ABT-267 and ABT-333 with or without RBV for 12 or 24 weeks.
Criteria for Evaluation:	
Efficacy: Plasma HCV RNA (IU/mL) will be assessed at each Treatment and Post-Treatment Visit. Clinical outcomes related to death and the liver will be assessed during treatment and post-treatment.
 
Patient Reported Outcomes (PROs): During treatment and post-treatment, fatigue and general health related quality of life will be assessed using the short form 36 version 2 (SF-36v2) and Functional Assessment of Chronic Illness Therapy – Fatigue (FACIT–F) questionnaires.
 
Safety: Safety and tolerability will be assessed by monitoring adverse events, physical examinations, clinical laboratory tests and vital signs.

Statistical Methods:	
Efficacy: Primary efficacy endpoint is the effect of response to treatment (assessed by SVR12) on clinical outcomes, based on subjects in this study and companion study TOPAZ II. The endpoint will be assessed by comparing the incidence of the following events between subjects who achieve SVR12 and those who do not using the Cox regression model:
 
 
• All-cause death
 
• Liver-related death
 
• Liver decompensation
 
• Liver transplantation
 
• Hepatocellular carcinoma
 
• Composite of any of the above outcomes
 
 
Secondary endpoint analyses:
 
 
• The long-term change from baseline in liver stiffness (as assessed by transient elastography [Fibroscan®]), when available, will be assessed by baseline fibrosis stage and sustained virologic response.
 
• The percentage of subjects achieving SVR12 and 2-sided 95% confidence interval will be presented by baseline fibrosis score (F0-F1, F2, F3 and F4).
 

---

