### **Secondary Objectives**

- To evaluate the long-term progression of fibrosis by baseline fibrosis stage and sustained virologic response, as measured by change from baseline in liver stiffness measured by transient elastography (FibroScan®) when available, in adults with genotype 1 (GT1) chronic HCV infection who received treatment with ABT-450/r/ABT-267 and ABT-333 with or without ribavirin.
- To evaluate the percentage of subjects achieving SVR12, with ABT-450/r/ABT-267 and ABT-333 with or without RBV in adults with GT1 chronic HCV infection.

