- r. Study drugs dispensed at Week 12 only for subjects in the 24-week arm.
- s. Historical or screening liver biopsy, FibroScan or FibroTest results will be used to determine the presence or absence of cirrhosis for the purpose of treatment assignment. FibroTest will be performed at Day 1, PT Week 12 during the post-treatment period. At sites where FibroScan is available, subjects will have FibroScan performed at Screening, End-of-Treatment Visit, and at all Post-Treatment Visits with the exception of PT Week 4.

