4.4 Planned Analysis

The primary analysis to evaluate the effect of response to treatment on clinical outcomes, will occur at the final analysis after all subjects have completed the study or prematurely discontinued the study. An interim analysis to assess the percentage of subjects achieving SVR₁₂ will occur after all subjects have completed the Post-Treatment Week 12 Visit or prematurely discontinued the study. For both final and interim analyses, data will be locked after performing appropriate data cleaning. Data after the interim analysis will be added to a subsequent version of the database. SAS[®] (SAS Institute, Inc., Cary, NC) for the UNIX operating system will be used for all analyses. All statistical tests and all confidence intervals will be two-sided with an α level of 0.05.

All analyses will be conducted by statisticians and statistical programmers at AbbVie or the designee according to the methodologies specified in this SAP.

There is no intention of shortening the follow-up time of subjects based on efficacy findings from the interim analysis. The intention is to follow all subjects who receive study drug for 260 weeks following treatment. There will be no statistical adjustment employed due to this interim analysis.

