6.3 Missing Data Imputation

No data will be imputed for any efficacy or safety analyses except for the PRO questionnaires, for analyses of the HCV RNA endpoints, and for analysis of the persistence of resistance. If a respondent answers at least 50% of the items in a multi-item scale of the SF-36v2, the missing items will be imputed with the average score of the answered items in the same scale. In cases where the respondent did not answer at least 50% of the items, the score for that domain will be considered missing. Similarly, the missing items of the FACIT-F questionnaire will be imputed with the average score of the answered items in the same scale as long as more than 50% (≥ 7 out of 13) of the items in the scale are answered. The SF-36v2 Mental and Physical Component Summary measures will not be computed if any domain is missing.

HCV RNA values will be selected for an SVR analysis based on visit windows as defined in Section 6.2. When there is no HCV RNA value in a visit window based on defined visit windows, the closest values before and after the window, regardless of the value chosen for the subsequent and preceding window, will be used for the flanking imputation described below.

If a subject has a missing HCV RNA value at a post-Day 1 visit but with undetectable or unquantifiable HCV RNA levels at both the preceding value and succeeding value, the HCV RNA level will be considered undetectable or unquantifiable, respectively, at this visit for this subject. In addition, if a subject has an unquantifiable HCV RNA level at the preceding value and an undetectable HCV RNA level at the succeeding value, or vice versa, the HCV RNA level will be imputed as unquantifiable at this visit for this subject. For SVR analyses, if there is no value in the appropriate window after flanking imputation but there is an HCV RNA value after the window, then it will be imputed into the SVR window. Subsequent to this flanking and backward imputation, if a subject is missing a value for the visit window associated with the analysis, the subject will be imputed as a visit failure (i.e., not undetectable or unquantifiable).

If a subject starts another treatment for HCV, then all HCV RNA and PRO assessment values for this subject measured on or after the start date of the new HCV treatment will be excluded from analyses. The subject will be considered a failure for summaries of viral response at all time points after the start of the new HCV treatment.

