10.3 Primary Efficacy Analysis

The primary efficacy analysis will be conducted among subjects in the ITT population as described in Section 5.1. HCV RNA values and SVR₁₂ will be imputed as described in Section 6.3.

The primary efficacy endpoint is to assess the effect of response to treatment (as assessed by SVR₁₂ status) on clinical outcomes by comparing the time to incidence of the following events between subjects who achieve SVR₁₂ and those who do not.

- All-cause death
- Liver-related death
- Liver decompensation
- Liver transplantation
- Hepatocellular carcinoma
- Composite of any of the above outcomes

For each of the six event types as listed above, a subject's time to event will be defined as the number of days from the first day of study drug to the day the subject experiences an event of interest. All events of interest will be included, regardless of whether the event occurred while the subject was still taking study drug or had previously discontinued study drug. However, events occurred after a subject started another treatment for HCV will be excluded and the subject will be censored at the time of starting the new HCV treatment. If the subject has not experienced an event of interest nor has the subject died (all-cause death), the subject's data will be censored at the date of the subject's last available assessment of clinical outcomes. All-cause death is a censoring event for liver-related death, liver decompensation, liver transplantation and hepatocellular carcinoma. For subjects with no post-baseline assessment, the subject's data will be censored on the first day of study drug. Time to the composite of clinical outcomes is the time to the first occurrence of any clinical outcome.

For each of the six event types, the distribution of time to event will be estimated for subjects who have achieved SVR₁₂ and those who haven't using Kaplan-Meier methodology and compared between the subjects who have achieved SVR₁₂ and those who haven't using the log-rank test.

For each of the six event types, the 1-, 2-, 3-, 4-, and 5-year event-free survival rate will be estimated using Kaplan-Meier methodology and a 95% confidence interval will be constructed separately for those who have achieved SVR₁₂ and those who haven't.

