10.4 Secondary Efficacy Analyses

The following analyses of secondary efficacy endpoints will be performed on the ITT-I population:

- The effect of sustained virologic response on change and percentage change from baseline in FibroScan score (assessed at the end of treatment and all post-treatment visits except PT Week 4) will be evaluated by comparing mean change from baseline at each applicable visit between subjects who achieve SVR₁₂ and those who do not using descriptive statistics and ANCOVA analyses. SVR₁₂ status will be included as a factor and baseline FibroScan score will be included as a covariate in the ANCOVA model. From the ANCOVA analyses, point estimates of the mean difference and 95% confidence intervals will be provided.
- Sustained virologic response will be evaluated using the percentage of subjects achieving SVR₁₂ (HCV RNA < LLOQ 12 weeks after the last actual dose of study drug). The simple percentage of subjects achieving SVR₁₂ will be calculated and a two-sided 95% confidence interval of the percentage will be computed based on Wilson's score method.

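### FibroScan has no rule for scans taken after a new HCV treatment, and the SAP reduces stiffness change by baseline fibrosis stage to cirrhosis yes/no

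*SAP*

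**What the plan says.** **New HCV treatment.** SAP 6.3 provides that after another HCV treatment starts, "all HCV RNA and PRO assessment values for this subject measured on or after the start date of the new HCV treatment will be excluded". For the primary clinical outcomes, SAP 10.3 drops later events, and "the subject will be censored at the time of starting the new HCV treatment". Neither rule mentions FibroScan.

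**FibroScan analysis.** SAP 10.4 covers end of treatment and every post-treatment visit except Week 4. The effect of response "will be evaluated by comparing mean change from baseline at each applicable visit between subjects who achieve" SVR12 and those who do not. In the model, SVR12 "status will be included as a factor and baseline FibroScan score will be included as a covariate in the ANCOVA model". Follow-up does not stop at retreatment: "The intention is to follow all subjects who receive study drug for 260 weeks following treatment" (SAP 4.4). Nor does scanning: where the device is available, "subjects will have FibroScan performed at Screening, End-of-Treatment Visit, and at all Post-Treatment Visits with the exception of PT Week 4" (Protocol Table 7, note s).

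**Fibrosis stage.** The first secondary objective in Protocol 4.0 is "To evaluate the long-term progression of fibrosis by baseline fibrosis stage and sustained virologic response", measured by change in liver stiffness. The synopsis says that this change "will be assessed by baseline fibrosis stage and sustained virologic response". Protocol 8.1.2.2 names both effects, although the comparison it spells out is by SVR12 status. SAP 4.1 restates the objective without stage, and the SAP 10.4 model has no stage term. SAP 10.5 applies the stiffness analysis to one subgroup, cirrhosis versus no cirrhosis, and adds a model with cirrhosis, SVR12 status and their interaction.

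**The concern.** SVR12 status is fixed at post-treatment Week 12, but the FibroScan comparison by that status runs to Week 260. Subjects without SVR12 are the ones most likely to receive another HCV treatment. If their later scans are kept, the late non-SVR12 mean mixes subjects still without a response with subjects who have been treated again. The objective concerns long-term progression, so the late visits matter most.

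On stage, the protocol introduction reports that stiffness improved most in patients with more advanced fibrosis at baseline. Change by stage is therefore part of the question. A two-level split answers only part of it.

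**Working it through.** The point rests on text, and the plan states no figure to reproduce. The arithmetic below gives scale only.

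**1. Handling after a new HCV treatment**

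| Outcome | Rule | Where |
|---|---|---|
| HCV RNA | values excluded; failure thereafter | SAP 6.3 |
| PROs | values excluded | SAP 6.3 |
| Clinical outcomes | later events excluded, subject censored | SAP 10.3 |
| FibroScan | none stated | SAP 6.3, 10.4 and 10.5 are silent |

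With no exclusion stated and all visits except post-treatment Week 4 in the analysis, the default is to keep the scans. End of treatment and post-treatment Week 12 are largely unaffected.

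**2. Direction.** Protocol 3.0 reports that stiffness fell during and after pegIFN/RBV therapy. If retreatment acts similarly, retained scans move the late non-SVR12 mean toward the SVR12 mean.

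**3. Scale.** Non-SVR12 in TOPAZ-I: 0.04 × 1650 = 66; SVR12: 1584. The documents give no retreatment rate, so r = 10, 20 or 40% per year is purely an assumption. Two cases are shown:

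- All non-SVR12 subjects are at risk of retreatment: s = 1.
- Only virologic failures are retreated. From the reported results of M11-646, M13-098 and M13-099 (12 and 24 weeks), non-SVR12 counts are 18 of 473, 11 of 297 (taken as 770 − 473), 17 of 208 and 7 of 172, total 53. Virologic failures are 8 + 7 + 13 + 4 = 32. So s = 32/53 = 0.604.

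Retreated share = s × [1 − (1 − r)^y]. Not yet retreated = 66 × (1 − share). If post-retreatment scans are excluded, the interval for the SVR12 difference widens by √[(1/left + 1/1584) / (1/66 + 1/1584)], assuming equal SDs.

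| s | Year | Share retreated (r = 10/20/40%) | Not yet retreated | Width factor |
|---|---|---|---|---|
| 0.604 | 3 | 16.4 / 29.5 / 47.3% | 55.2 / 46.6 / 34.8 | 1.090 / 1.184 / 1.365 |
| 0.604 | 5 | 24.7 / 40.6 / 55.7% | 49.7 / 39.2 / 29.2 | 1.147 / 1.287 / 1.485 |
| 1 | 3 | 27.1 / 48.8 / 78.4% | 48.1 / 33.8 / 14.3 | 1.165 / 1.384 / 2.118 |
| 1 | 5 | 41.0 / 67.2 / 92.2% | 39.0 / 21.6 / 5.1 | 1.291 / 1.723 / 3.519 |

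Counts are before dropout and assume every subject is scanned. If 75, 50 or 25% have FibroScan, the starting 66 becomes about 50, 33 or 17. The share retreated is not the bias. It would equal the proportional shrinkage of the difference only if every retreated subject had moved all the way to the SVR12 mean and had otherwise been like the rest.

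**4. Use of baseline stage in the SAP**

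| Endpoint | Stage used |
|---|---|
| SVR12 rate (SAP 10.5) | F0-F1, F2, F3, F4 |
| PROs, exploratory (SAP 10.9) | baseline fibrosis stage, SVR12 and their interaction |
| FibroScan (SAP 10.4) | none |
| FibroScan (SAP 10.5) | cirrhosis yes/no |

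**5. Cell sizes.** The enrolment figures are caps, so stage sizes cannot be derived. If both caps fill (1000 F0-F1, 400 F4), 1650 − 1400 = 250 remain for F2 and F3 together. At 4% in every stage (an assumption), non-SVR12 counts are 40 in F0-F1, 10 in F2 and F3 combined, and 16 in F4. At the M13-099 non-SVR12 rates, F4 gives 400 × 0.041 = 16.4 to 400 × 0.082 = 32.8.

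**The case against.** **On retreatment.** The SAP lists what is cut and FibroScan is not listed, so the text does yield a default. Analysing all observed data is a legitimate choice. Excluding post-retreatment scans conditions on not being retreated, which may depend on disease severity, and it costs precision: up to a 3.519-fold wider interval in the most extreme illustration. The assumed retreatment rates have no source in the documents, and the 0.604 share uses only three of the six Phase 3 studies. All of this stands, so keeping the scans should not be called an error. What it does not answer is that the choice is unstated and differs from the handling of the primary outcomes under the same SVR12 split.

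**On stage.** A reader might infer that the report would show nothing by stage, or no SVR12 contrast within disease severity. The documents do not support that. SAP 10.5 first applies the SAP 10.4 SVR12 comparison to the cirrhosis subgroup and then fits the interaction model. Cirrhosis is F4 by the protocol's definition, so the most advanced stage is shown against the rest. Nor does the objective itself name four levels; those come from Protocol Table 4 and 8.1.1. Protocol 8.1.2.3 leaves stiffness subgroups to what is appropriate and useful. Non-SVR12 cells in F2 and F3 would be sparse, so collapsing for a formal comparison is defensible. Running the subgroup on mITT-I-GT rather than ITT-I is minor, since it removes only subjects who are not genotype 1. What remains is that F0-F1, F2 and F3 are merged for an endpoint whose objective names stage, and sparse cells do not prevent a descriptive table.

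**Conclusion.** Both gaps are real and both are limited.

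(1) The SAP does not say whether FibroScan values after a new HCV treatment count. As written they do, which is inconsistent with the primary comparison and probably biases the late SVR12 difference toward zero. The direction assumes that retreatment lowers stiffness, as the protocol reports for pegIFN/RBV. A reader might take the shares above as the size of the bias. They are not: without a retreatment rate the bias cannot be computed.

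(2) The SAP carries out the stage part of the objective only as F4 versus F0-F3. The loss is resolution among F0-F1, F2 and F3, not the absence of any analysis by severity.

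This concerns one secondary endpoint and leaves the primary analysis untouched. The SAP should be changed before the final analysis. Confidence is medium.

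**What to change.** 1. In SAP 6.3 and 10.4, report the FibroScan comparison by SVR12 status in two ways: excluding values on or after the start of a new HCV treatment, and using all observed values. State in advance which is the main one. Show the number of non-SVR12 subjects contributing at each visit.
2. In SAP 10.4, add a descriptive summary on ITT-I of FibroScan change from baseline by stage (F0-F1, F2, F3, F4) and SVR12 status at each visit. Make no formal SVR12 comparison in a stage where a cell has fewer than 10 subjects, borrowing the threshold that SAP 10.5 sets per subgroup. A stage term in the ANCOVA is not needed: baseline FibroScan is already a covariate, and stage may itself be derived from FibroScan (Protocol Table 4).

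The cost is SAP wording and programming. Anti-HCV medications are collected throughout the post-treatment period (Protocol 5.2.3, SAP 7.3), SAP 10.3 already needs the start date of a new treatment, and the four-level stage variable exists. The downside of the exclusion analysis is fewer late non-SVR12 values and possible selection, which is why the all-observed analysis belongs beside it.

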HCV RNA < LLOQ Analyses for SVR

If a subject is missing an HCV RNA value for the visit window associated with the analysis of SVR after performing the imputations described above, then this value will be imputed with an HCV RNA value from a local laboratory if present; otherwise, the HCV RNA value for this visit will be missing. Subjects with missing HCV RNA data in the analysis window, after imputations, will be imputed as a failure.

HCV RNA Analyses for Relapse and Virologic Failure

If HCV RNA values from the central laboratory are missing but a local laboratory value is present in the appropriate time period, then the local laboratory value will be used to assess post-treatment relapse and on-treatment virologic failure.

Finally, missing sequence data will be imputed as follows in the analysis of the persistence of resistance from the sequences from PT Week 52 through PT Week 260 (5 years). If a signature variant is not detectable by population, clonal or deep sequencing at PT Week 24 (or later), the variant is imputed as not detectable at the PT Week 52 (or timepoints after the sequence with the variant not detectable) and time points thereafter if a sample from Post-Treatment Week 52 or later is not sequenced. If a signature variant is detectable by population, clonal, or deep sequencing at Post-Treatment Week 52 or later, then the variant is imputed as being detectable at earlier time points if the sample at the earlier time point is not sequenced.

7.0 Demographics, Baseline Characteristics, Medical History, and Previous/Concomitant Medications

Demographics, baseline characteristics, medical history, and previous/concomitant medications will be summarized overall and by presence of cirrhosis and genotype 1 subtype on the safety population.

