The number and percentage of subjects with post-baseline variants at signature amino acid positions or emerged variants at non-signature amino acid positions by, listed by amino acid position and variant within a DAA target at the time of VF compared to baseline will be summarized, along with the number of subjects within a DAA target and overall. The analyses will be grouped by HCV subtype (1a or 1b) and DAA target (NS3, NS5A, or NS5B) and will list the subject numbers of subjects with each variant. The number of subjects with resistance variants in 3 targets, 2 targets or 1 target will be provided.

Listings by subject and time point of all post-baseline variants relative to the baseline amino acid sequence will be provided for each DAA target (NS3, NS5A, and NS5B). In addition, a listing by subject and time point of all post-baseline variants at signature resistance-associated amino acid positions relative to the appropriate prototypic reference amino acid sequences will be provided.

For all subjects who experience VF, the persistence of resistance-associated variants for each target (NS3, NS5A, and NS5B) will be assessed by NGS at Post-Treatment Weeks 24 and 52 and at time points up to Post-Treatment Week 260 (5 years). The number and percentage of subjects with post-baseline variants at signature amino acid positions, listed by amino acid position and variant within a DAA target at each Post-Treatment time point compared to baseline will be summarized, along with the number of subjects within a DAA target and overall. Additionally, the number and percentage of subjects in whom a signature variant persisted at Post-Treatment Week 24 and 52 and time points up to Post-Treatment Week 260 (5 years) out of the total number of subjects with that emerged variant at the VF time point and at that time point will be summarized by DAA target, and variant. The number and percentage of subjects who still have a variant at a given Post-Treatment time point will be calculated out of all subjects with that variant at VF who have sequencing at that time point. The imputation described below will be used for PT Week 52 or time points up to Post-Treatment Week 260 (5 years). If a

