signature variant is not detectable at Post-Treatment Week 24, the variant is imputed as not detectable at the Post-Treatment Week 52 and time points thereafter even if a sample from Post-Treatment Week 52 or later is not sequenced. If a signature variant is detectable at Post-Treatment Week 52 or later, then the variant is imputed as being detectable at earlier time points even if the sample at the earlier time point is not sequenced.

If resistance-associated variants are not detected by NGS in a given target for a subject either at the time of failure or in a post treatment sample, then that target will not be sequenced in subsequent samples from that subject.

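### The resistance-persistence imputation carries a lost variant forward past dropout and retreatment, while subjects last seen with the variant leave the calculation

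*SAP*

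**What the plan says.** SAP Section 6.3 has two rules for missing sequence data, and Section 10.8 repeats them.

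- **Forward rule.** After a non-detection from PT Week 24 onward, "the variant is imputed as not detectable at the PT Week 52". Subsequent visits get the same value, under this condition: "and time points thereafter if a sample from Post-Treatment Week 52 or later is not sequenced". The rule fills only visits without a sequence, and does not require that the subject is still in the study or free of new HCV treatment.
- **Backward rule.** A detection from PT Week 52 onward works in the other direction: "then the variant is imputed as being detectable at earlier time points if the sample at the earlier time point is not sequenced". No rule carries a detection forward.

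Section 10.8 adds three things:

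- **A stop rule.** Once resistance variants are not detected in a target, "then that target will not be sequenced in subsequent samples from that subject".
- **A denominator.** The persistence percentage is "calculated out of all subjects with that variant at VF who have sequencing at that time point".
- **The instruction that follows it.** "The imputation described below will be used for PT Week 52 or time points up to Post-Treatment Week 260 (5 years"). The SAP does not say whether a subject with an imputed value, and so no sequence at that visit, enters the denominator.

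Elsewhere the SAP does react to new HCV treatment. Section 6.3 excludes later HCV RNA and PRO values, and Section 10.3 censors the clinical outcomes at that date. The persistence rules have no equivalent.

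**The concern.** Take two subjects who leave at PT Week 60. The first had lost the variant by PT Week 24 and is counted as not detectable through PT Week 260. The second still carried it at PT Week 52 and contributes nothing afterwards. If imputed values are counted, subjects who lost the variant early accumulate in the denominator while carriers drop out of it.

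Retreatment is a foreseeable reason for carriers to leave. The SAP plans to summarise post-treatment HCV medication (Section 7.3). It sequences only samples with HCV RNA of at least 1000 IU/mL (Section 10.8), so a carrier who is retreated and suppressed yields no further sequence.

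At stake is the planned five-year description of how long resistance variants last after virologic failure (Protocol synopsis, Resistance; Protocol Section 8.1.3; SAP Section 10.8).

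**Working it through.** The documents state no persistence figure, so there is none to reproduce. The check applies the rules to assumed rates.

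**Inputs from the documents.** Post-treatment visits at Weeks 24, 52, 104, 156, 208 and 260. Dropout of up to 20% (SAP Section 4.3, a whole-trial planning figure). 4% without SVR12 (same section): 0.04 × 1650 = 66 subjects in this study, an upper guide because not every non-responder is a virologic failure.

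**Assumptions.** All subjects considered carry the variant at the end of treatment. Loss is one-way and exponential with median m weeks. Leaving (dropout or retreatment) is exponential and unrelated to the variant. No other visits are missed. The documents give neither rate for virologic failures.

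Let S(t) = 0.5^(t/m) be true persistence, G(t) the share still followed and not retreated, v1 to v6 the visits, and v0 = 0.

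**Reading A: imputed subjects counted.**

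Reported(vk) = S(vk)G(vk) / [S(vk)G(vk) + Σ over j ≤ k of (S(v(j−1)) − S(vj))·G(vj)]

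The fault is that each lost-variant term keeps G at the visit where loss was seen, while carriers are reduced to G at the current visit.

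Example: m = 104, 50% leaving by PT Week 104, read at PT Week 104.

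- Detectable: 0.5 × 0.5 = 0.2500
- Lost, seen at Week 24: 0.1478 × 0.8522 = 0.1260
- Lost, seen at Week 52: 0.1451 × 0.7071 = 0.1026
- Lost, seen at Week 104: 0.2071 × 0.5 = 0.1036
- Reported: 0.2500 / (0.2500 + 0.3321) = 42.9%, against a true 50.0%

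The same formula gives:

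| Leaving | Median (weeks) | PT Week | Reported | True |
|---|---|---|---|---|
| 20% by Week 260 | 52 | 104 | 24.3% | 25.0% |
| 20% by Week 260 | 104 | 208 | 23.3% | 25.0% |
| 20% by Week 260 | 260 | 260 | 47.3% | 50.0% |
| 20% by Week 104 | 52 | 104 | 23.2% | 25.0% |
| 50% by Week 104 | 52 | 104 | 19.4% | 25.0% |
| 50% by Week 104 | 52 | 260 | 0.9% | 3.1% |
| 50% by Week 104 | 104 | 156 | 24.6% | 35.4% |
| 50% by Week 104 | 104 | 208 | 13.2% | 25.0% |
| 50% by Week 104 | 260 | 260 | 28.1% | 50.0% |

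With 20% leaving by PT Week 260 the gap stays below 3 points. With 50% leaving by PT Week 104 and medians of 52 to 260 weeks, it runs from 2.2 points (3.1 − 0.9) to 21.9 points (50.0 − 28.1) at PT Week 104 and later. With nobody leaving, G = 1 and the formula returns S(vk) exactly.

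**Reading B: only sequenced subjects counted.** Under the stop rule, the only lost-variant subjects sequenced at vk are those who lost it since the previous visit. G cancels:

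Reported(vk) = S(vk) / S(v(k−1))

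For m = 104 at PT Week 104: 0.5 / 0.7071 = 70.7%, against 50%. For m = 52: 0.25 / 0.50 = 50%, against 25%.

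**Check of the repair.** If non-detection is carried only to visits at which the subject is still followed and not retreated, every G(vj) in reading A becomes G(vk). The sum becomes (1 − S(vk))·G(vk), and the ratio is S(vk).

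**Check of the mirror-image repair.** If detection is also carried forward, a simulation with 20% dropout by PT Week 260 gives 55.6% against a true 50% at that visit. With 50% dropout it gives 64.7%.

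**The case against.** The best defence is that the forward carry has a reason. The stop rule leaves followed subjects without later sequences by design, and without the carry they would vanish from the percentage although their variant had gone. Under one-way loss, which both imputation rules presume, the carry is correct for them. That stands, and limits the point to gaps after dropout or new treatment.

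It can also be said that the documents do not fix the direction of the error. That stands too. A reader might infer that the plan simply makes variants appear to fade too fast. That holds only if imputed subjects are counted. This is the likelier reading, because otherwise the forward imputation would not affect the percentage, but Section 10.8 does not say so, and its literal denominator errs the other way.

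The larger figures depend on 50% leaving by PT Week 104, which has no source in the documents. That virologic failures leave faster than the trial-wide 20% is plausible but unquantified.

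Little depends on the result. At most about 66 subjects are split by target and variant. With 20 carriers of a variant, one subject is 5 points, more than the error at 20% leaving by PT Week 260. A reader might take persistence for a study objective, but Protocol Section 4.0 and SAP Section 4.1 do not list resistance.

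**Conclusion.** The concern holds in a limited form. The SAP treats gaps made by its stop rule and gaps after dropout or retreatment alike, and only the first kind justifies carrying non-detection forward.

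With imputed subjects counted, late persistence is understated by under 3 points if 20% leave by PT Week 260. If 50% leave by PT Week 104, the understatement is roughly 2 to 22 points at PT Week 104 and later for median persistence of 52 to 260 weeks. With sequenced subjects only, persistence is strongly overstated. All sizes rest on assumed exponential loss, one-way loss and leaving unrelated to the variant.

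Because detection is never carried forward, a reader might conclude that it should be. That would replace an understatement with an overstatement.

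This is a minor, cheap correction to a descriptive summary. The primary analysis and the secondary endpoints are unaffected.

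**What to change.** In SAP Sections 6.3 and 10.8:

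1. Carry non-detection forward only to visits at which the subject is still followed and has not started new HCV treatment.
2. State that these imputed subjects count in the persistence denominator of Section 10.8.
3. Do not carry detection forward.
4. Align the two sections: 6.3 starts the forward rule at PT Week 24 or later and names population, clonal or deep sequencing, while 10.8 starts it at PT Week 24 and uses NGS.

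An acceptable alternative is a time-to-loss curve for each variant: Kaplan-Meier on the first negative sample, censored at the last sequenced sample before leaving or retreatment. An interval-censored version is optional in so few subjects.

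The repair does not remove the effect of missed visits. In a simulation with almost no dropout, 15% of visits missed at random and a true value of 49.9% at PT Week 260, the carry gives 46.5%. The number sequenced, imputed and missing should therefore be shown at each visit.

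The cost is SAP wording and minor programming on data already collected.
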